Visit 2 (Sacral Nerve Stimulator Lead Placement): Surgery for stage 1 sacral nerve stimulator placement will occur within 30 days after enrollment in the study. The patient will arrive at the pre-operative holding areas at UTMDACC's main campus for their outpatient surgery. The representative for the implantable SNS company (Medtronic) will be present at the operation for assistance with placement of the leads per standard of care and for assistance with patient education following lead placement. The patients are sent home with a diary to record daily bowel and bladder habits during the interval period.

Visit 3 (Assessment of Symptoms and Battery Implantation or Lead Removal): Surgery for stage 2 sacral nerve stimulator battery implantation or lead removal will occur around 2 weeks (+7 days) after SNS placement. The patient will arrive to the holding area with their post-implantation bowel and bladder habit diary from visit 2. Review of the bowel diary information and a review of symptoms from visit 1 and visit 2 with the patient will be completed and then a decision made to either implant the battery or remove the stimulator leads as per standard of care. If the bowel diary reveals $\geq 50\%$ decrease in FI or LARS symptoms between visit 1 and visit 2, the external temporary battery will be replaced with an implantable battery. If the bowel diary reveals $< 50\%$ decrease in FI or LARS symptoms, the previously placed leads and external battery will be evaluated for proper positioning and functioning in the OR and removed if they remain properly positioned. Following the procedure, the patient is discharged home. If the device is removed, their participation in the study is complete, but data collected to this point will still be used in study analysis and reporting.

Visit 4 (Post-operative Assessment): Post-operative evaluation. The patients return to clinic at 1 month (+/- 2 weeks) after completion of visit 3 for a wound evaluation, device check, and symptom review. At this point, the patients will complete study questionnaires (on paper, over the phone/teleconference system, or electronically through REDCap) and undergo a repeat ARM.

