6.3. Endpoints

Primary Endpoints

The primary endpoint is SNS Success. *SNS Success* will be measured as a patient having the battery implanted at visit 3 which can only happen if they've achieved improvement in fecal incontinence at visit 3. Patients who do not have the SNS placed, for any reason other than insurance coverage issues, will count as not having a success.

Fecal incontinence will be measured by the physician as the total number of gas, mucus, liquid stool, and solid stool accidental leakage events reported in the bowel diaries.

Improvement will be determined by the physician based on bowel diary comparisons recorded before SNS lead placement at visit 1 to after lead placement at visit 2. This is done at visit 3 when the patient presents for consideration of placement of the implantable battery. Any patient who comes in for SNS placement but the SNS cannot be successfully placed for any reason other than insurance reasons will count as not having improvement. Patients meeting this improvement will have their *battery implanted*. Patients will be counted as having their battery implanted if it is implanted at Visit 3 if they had the SNS placed at Visit 2.

Secondary Endpoints

- **FISI** overall questionnaire summary
- **FIQOL** overall questionnaire summary
- **ARM** score
- **EQ-5D-5L**
- **ICSmaleSF** or **ICIS-FLUTS** (females)
- **MSKCC BFQ (for restorative surgery cohort)**
- **LARS Score Bowel Function Questionnaire (for restorative surgery cohort)**

- **CCIS (for radiation only cohort)**
- **Bowel Diaries**
- **Bladder Diaries**
- **EORTC QLQ-CR29**
- **FISI, FIQOL, EQ-5D-5L, ICSmaleSF or ICIS-FLUTS, MSKCC, EORTC QLQ-CR29 and CCIS will also be collected at 1 and 3 years for long-term evaluation.**

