6.6. Analysis Plan

The proportion of patients who experience SNS success will be reported with a 90% credible interval using a beta(1,1) prior for each cohort. For the patients in the reconstruction cohort, a success rate of 50% or better will establish confirmation of efficacy of SNS implant that would warrant offering SNS implant to alleviate bowel symptoms following anal reconstruction. In the chemoradiation therapy only cohort, a success rate of 50% or better would warrant studying SNS implant further in this patient population. The secondary measures will be reported descriptively with graphs or tabulations for categorical survey outcomes, CLEs, and anorectal manometry measures. Exploratory logistic regression models will be performed to identify patients who may be more likely to have SNS success using baseline measures and visit 2 bowel/bladder diaries. Analysis of SNS success, safety, and measures up through visit 4 measures will be completed and published once all patients are enrolled and complete the first 4 visits or are off study. Additional analyses will be completed and published after the long-term 1 and 3 year follow-up questionnaires are completed.

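### Section 6.6 looks for predictors of benefit only through implanted yes/no, although leakage counts are recorded before and after lead placement; an exploratory log-count model beside it is a cheap improvement

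*Combined protocol and SAP*

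**What the plan says.** Section 6.6 plans one kind of predictor analysis: "Exploratory logistic regression models will be performed to identify patients who may be more likely to have SNS success". It gives no other model for who benefits. The predictors for these models are to be found "using baseline measures and visit 2 bowel/bladder diaries". The remaining secondary measures, which under Section 6.3 include the bowel diaries, are to be described only.

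Section 6.3 defines the outcome of those models: SNS Success "will be measured as a patient having the battery implanted at visit 3". It also defines a quantitative measure, fecal incontinence as "the total number of gas, mucus, liquid stool, and solid stool accidental leakage events reported in the bowel diaries", and says that the physician judges improvement from "bowel diary comparisons recorded before SNS lead placement at visit 1 to after lead placement at visit 2".

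Section 5 (Visit 3) sets the implant criterion as at least a 50% "decrease in FI or LARS symptoms between visit 1 and visit 2". The diary and symptoms are reviewed, "then a decision made to either implant the battery or remove the stimulator leads as per standard of care". Table 1 schedules the bowel diary at visits 1 and 2, so a post-lead count should exist for tested non-responders as well as responders.

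Section 6.4 caps each cohort at 30. Nothing says whether the predictor models are fitted per cohort or pooled.

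**The concern.** A yes/no outcome treats a 52% and a 100% reduction in leakage as the same result, and 48% and 52% as opposites. Section 2 cites 50% improvement as the accepted marker of success. That supports the binary primary endpoint and explains the implant criterion, but it is no reason to set the counts aside when looking for predictors.

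Small cohorts make this matter more. At the 79.1% implantation rate quoted in Section 2, 30 patients give 30 × (1 − 0.791) ≈ 6 failures, which will hardly support more than one predictor in a logistic model.

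The same sentence of Section 6.6 has a second problem. It lists the visit 2 diaries as predictors, but the visit 2 bowel diary is half of the comparison that decides success. A model using it would largely rediscover the implant criterion, and with about 30 patients it risks near-separation.

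What is at stake is a real predictor going unseen in an exploratory analysis. The primary result is not affected.

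**Working it through.** **The plan's own figure.** With 15/30 successes and a beta(1,1) prior the posterior is Beta(16,16). Its 5th and 95th percentiles are 35.66% and 64.34%, matching Section 6.4. That figure concerns the primary endpoint; there is no stated power for the predictor models to reproduce.

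**Inputs from the documents.** n up to 30 per cohort, with 24 the last interim look (6.4, 6.5); success rate 50% (6.4) or 79.1% (Section 2).

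**Assumed, because the documents are silent.** Two-sided 5%; predictor strength; spread and size of the diary counts; models fitted within a cohort.

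**1. Formula check.** Take a 1:1 baseline factor shifting a normal improvement score by d standard deviations, with success a cut of that score.

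- Full scale: power = Φ(d√(n/4) − 1.96). For n = 30, d = 0.8: Φ(2.191 − 1.96) = Φ(0.231) = 59.1%.
- Yes/no at 50% success: p₁ = Φ(0.4) = 0.655, p₂ = 0.345, difference 0.311. Power = Φ([0.311 − 1.96√(2 × 0.25/15)] / √(2 × 0.655 × 0.345/15)) = Φ((0.311 − 0.358)/0.174) = Φ(−0.271) = 39.3%.
- Loss: 59.1 − 39.3 = 19.8 points.

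Over n = 24 or 30, d = 0.5 to 1.0 and success 30% to 70%, the loss is 7.6 to 28.8 points. At 79% success it is 10.2 to 36.6, reaching 40.1 at n = 24, d = 1.2. If counts are usable in only 24 of 30 patients while the yes/no analysis keeps all 30, the loss is 4.6 to 19.4 (d 0.5 to 1.0, success 50% to 70%).

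**2. Diary-count simulation.** This is closer to the data. Baseline counts are Poisson with a gamma-distributed mean averaging 16. The post-lead mean is the baseline mean × exp(μ − βx + N(0,1)), and the patient is implanted if the post-lead count is at most half of baseline. The log-count linear model, adjusted for log baseline, is compared with the logistic likelihood-ratio test; 3,000 datasets per setting. The values β = 0.3, 0.5, 0.7 correspond to correlations β/√(β² + 1) = 0.29, 0.45, 0.57 with the true log effect.

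| n | β | success % | log-count power % | logistic power % | loss |
|---|---|---|---|---|---|
| 24 | 0.3 | 51.0 | 20.9 | 19.0 | 1.9 |
| 30 | 0.5 | 50.6 | 57.9 | 44.5 | 13.4 |
| 30 | 0.5 | 77.2 | 51.7 | 37.7 | 14.0 |
| 30 | 0.7 | 75.3 | 79.2 | 61.5 | 17.7 |

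The full non-null range is 1.9 to 17.7 points with complete counts. It is 3.4 to 28.6 when a random 10% have no post-lead count and are scored as failures. Under no effect, with complete counts, the log-count model rejected 4.6% to 5.9% and the logistic test 5.9% to 6.9%, so the comparison slightly favours the logistic test.

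**3. Second diary-count simulation.** With an assumed median of 14 events per diary and correlation 0.3 to 0.5 with the true log effect, the log-count model gained in every non-null setting, by about 1 to 19 points. A smaller set of 600 datasets per setting gave about 0 to 14. A negative binomial Wald test rejected about 11% to 12% under no effect, roughly twice the nominal level.

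**Range.** About 1 to 19 points under step 3; about 2 to 40 across steps 1 and 2.

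**The case against.** The strongest reply is that Section 6.6 asks who is likely to reach SNS Success, and logistic regression answers exactly that. The models are labelled exploratory, no power is claimed, and the diaries are already reported descriptively. This stands: the logistic model should not be demoted, and nothing stated in the plan is in error.

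A second reply is that success is not a pure cut of the leakage count. The physician judges it, Section 5 refers to FI or LARS symptoms while Section 6.3 counts leakage, and patients with no SNS placed (insurance reasons aside) are failures without a post-lead count. This also stands. A patient with little leakage could be implanted for relief of other symptoms, and a leakage model would miss that benefit. The two descriptions in Sections 5 and 6.3 should be reconciled; which is right is not for this review.

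A third reply is that the gain may be negligible for a weak predictor. The low end of the simulations agrees.

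Two stronger readings are tempting. A reader might take one grid, such as 8 to 29 points, as the known cost of the plan. The documents supply neither the effect size, the diary variability nor the alpha that would fix such a figure. A reader might also infer that these models will steer patient selection in a later trial. Section 2 mentions only a wider population and an efficacy arm for radiation-only patients, and the go-forward criterion in Section 6.6 is the 50% success rate.

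**Conclusion.** The point holds as a missed opportunity. The only planned predictor models use implanted yes/no while paired leakage counts go unmodelled, and one listed predictor, the visit 2 bowel diary, is part of the outcome's definition.

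The direction of the power loss is well supported. Its size is conditional: about 1 to 19 points for 24 to 30 patients, two-sided 5%, a predictor correlation of 0.3 to 0.5 with the true log effect and the assumed counts, and about 2 to 40 under other assumptions. If no baseline factor matters, nothing is lost. If the cohorts were pooled to 60, the formula in step 1 gives about 11 to 33 points for d 0.5 to 1.0 and success 50% to 79%.

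This does not touch the primary endpoint, the stopping rules or any published figure. Label: cheap improvement.

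**What to change.** In Section 6.6:

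- Keep the exploratory logistic model of SNS Success. Alongside it, add an exploratory linear model of log(post-lead leakage rate + constant) on each baseline predictor, adjusted for log(baseline rate + constant), in all patients with a test-phase diary. Use events per diary day, since recording periods can differ, and fix the constant in advance.
- Use baseline predictors only in the new model. Remove the visit 2 bowel diary from the predictors of the logistic model.
- Do not use a negative binomial Wald test at this sample size, given its excess of false positives in simulation.
- State whether the models are fitted per cohort or pooled.
- Leave the binary primary endpoint and its 90% credible interval unchanged.

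The cost is a few lines of SAP text and one model on data already collected. The downside is coverage: patients with no lead placed have no post-lead count, and patients treated mainly for LARS symptoms with little leakage add little information. Both groups remain represented through the logistic model.

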After 2 weeks, the patients return to the OR for either removal of the leads if the stimulator did not work, or implantation of a subcutaneous titanium battery with internalization of the electrode as per standard of care. Prior to lead extraction in patients who do not meet criteria for battery implantation, lead position will be re-investigated for appropriate positioning, and if incorrectly positioned due to migration, lead repositioning will be performed and the two week trial period restarted. The patients are discharged home from this outpatient surgery and will complete the bowel and bladder habit diaries. The patients will be required to return to the office at 1 month following their surgery to perform a wound check, symptom evaluation, and again complete study questionnaires (on paper, over the phone/teleconference system, or electronically through REDCap) for comparison, and undergo repeat anorectal manometry and a post-void residual bladder scan.

Validated Questionnaires/Instruments:

1. Fecal Incontinence Quality of Life (FIQoL): this is a quality of life instrument validated for patients with fecal incontinence. This will be provided to all patients.
2. Fecal Incontinence Severity Index (FISI): this is a scoring system validated to objectively quantify fecal incontinence severity. This will be provided to all patients.

3. EQ-5D-5L: This is a general quality of life instrument that is currently used in the GI surgery clinics as part of the prospective rectal cancer study that collects longitudinal quality of life and function outcomes. This will be provided to all patients.
4. Memorial Sloan Kettering Cancer Center Bowel Function Instrument (MSKCC BFI): This is a validated instrument for resected rectal cancer patients designed to assess bowel dysfunction including LARS. This will be provided to patients in the restorative surgery cohort only.
5. Cleveland Clinic Incontinence Score (CCIS): This is a validated instrument for FI specifically in patients whose rectums have not been surgically removed. This will be provided to the radiation only cohort patients.
6. Bowel Diary: Validated bowel diary provided by the device company used to collect daily bowel function.
7. Bladder Diary: Validated urinary diary provided by the device company used to collect daily urinary function.

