6.2. Analysis Subgroups

All patients who sign consent and take the visit 1 questionnaires, and do not have insurance denial as the reason for no SNS placement, will be considered evaluable for this study. Patients who return for their SNS placement appointment will be included in analyses of the endpoints.

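### The exploratory models of SNS success use the post-lead visit 2 bowel diary as a predictor, although that diary is one of the two inputs that decide success

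*Combined protocol and SAP*

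**What the plan says.** **Outcome.** Section 6.3 (Endpoints) defines SNS success as having the battery implanted at visit 3. The physician judges improvement "based on bowel diary comparisons recorded before SNS lead placement at visit 1 to after lead placement at visit 2". Section 6.3 measures incontinence as the total number of leakage events in the bowel diaries.

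**Decision rule.** Section 5 (Study Visits, Visit 3) implants the battery "If the bowel diary reveals $\geq 50\%$ decrease in FI or LARS symptoms between visit 1 and visit 2".

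**Which diary is meant.** Under Visit 2, after lead placement, "The patients are sent home with a diary to record daily bowel and bladder habits during the interval period". The Visit 3 text calls this the post-implantation diary, and Table 1 schedules diaries only at visits 1 and 2. The visit 2 diary is thus the one kept during test stimulation.

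**Predictors.** Section 6.6 (Analysis Plan) fits exploratory logistic models "to identify patients who may be more likely to have SNS success using baseline measures and visit 2 bowel/bladder diaries". It does not mention the overlap with the endpoint. It does not say which diary items enter, whether both bowel diaries enter one model, or whether the cohorts are pooled.

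**Failures without a diary.** Section 6.3 counts as not improved "Any patient who comes in for SNS placement but the SNS cannot be successfully placed for any reason other than insurance reasons". Section 6.2 adds that "Patients who return for their SNS placement appointment will be included in analyses of the endpoints".

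**The concern.** The aim in section 6.6 is to find patients who are more likely to succeed. A predictor that is part of the success rule cannot serve that aim: a low post-lead leakage count goes with success largely because success is defined by a low post-lead count relative to baseline. A published table could present this as a clinical finding, or the fitting could break down without an obvious reason.

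Two further problems follow from timing. The diary exists only once the lead is in, so it cannot guide selection before surgery. And patients whose lead could not be placed are failures with no post-lead diary, so any model using it drops them and describes a different population from the primary endpoint.

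**Working it through.** **1. The plan's own figures.** The plan attaches no number to these models. Its nearest figure concerns the same endpoint: 15 successes in 30 with a beta(1,1) prior gives Beta(16,16), whose 5% and 95% quantiles are 35.7% and 64.3%, as section 6.4 states. Nothing below alters it.

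**2. The overlap.** Let B be the visit 1 bowel value and P the post-lead (visit 2) bowel value.

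- Success (section 6.3 with the Visit 3 rule): (B − P)/B ≥ 0.50, that is, P ≤ 0.5B.
- Predictors (section 6.6): baseline measures, which would include B, and the visit 2 diary, which contains P.

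For any fixed B, lowering P moves a patient towards success by definition.

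**3. When separation is certain.** Put L = 0.5B − P. Under the strict rule every success has L ≥ 0 and every failure L < 0. Let −d be the largest L among the failures (d > 0). Then L + d/2 is positive for every success and negative for every failure. Multiplying this score by an ever larger constant keeps raising the likelihood, so no finite maximum exists. As an example with an assumed B = 14: P = 7 gives L = 0 and success (decrease 7/14 = 50%), while P = 8 gives L = −1 and failure (6/14 = 42.9%).

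This needs three conditions: the rule applied strictly, both values in one model, and the model on the scale the rule uses (totals if totals are compared, rates if rates are).

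**4. What loosens it.** Section 6.3 leaves the determination to the physician. The Visit 3 text refers to FI or LARS symptoms rather than leakage alone. Section 6.5 recognises lead removal for reasons other than failure. The scale could also differ from the rule's: section 5 gives the post-lead diary about 2 weeks, and if the lead has migrated, "lead repositioning will be performed and the two week trial period restarted". The baseline length is not fixed, since "Surgery for stage 1 sacral nerve stimulator placement will occur within 30 days after enrollment in the study". Each makes complete separation less frequent; none removes step 2.

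**5. Illustration only; every input is assumed.** Cohorts of 30; weekly leakage rate gamma (mean 7.5, shape 2) plus 0.5; treatment rate ratio log-normal (median 0.35, 0.5 or 0.6; log-SD 0.6), independent of baseline; Poisson counts over two 14-day diaries.

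| Setting | Result |
|---|---|
| Strict rule, both counts in one model | complete separation in 100% of cohorts |
| 10% of diary successes turned into failures | separation in roughly 15–39% |
| 10% of outcomes flipped either way | separation in roughly 5–11% |
| Strict rule, visit 2 count alone | AUC about 0.79–0.85 |
| Strict rule, visit 1 value alone | AUC about 0.53–0.59 |
| As above, plus baseline-period fluctuation of log-SD 0.8 | AUC about 0.75 for each diary alone |

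Under a different assumed model in which the two counts are generated independently, the AUC is 0.85–0.87 for visit 2 and 0.79–0.82 for visit 1. Both inputs are therefore coupled to success. How the coupling divides between them depends on within-patient fluctuation, which the documents do not give.

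**6. Missing diaries.** The number of attending patients in whom the lead cannot be placed cannot be derived from the documents.

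**The case against.** The strongest defence is that the plan calls these models exploratory and no decision uses them. That stands, and it sets the severity. It does not make a partly definitional association informative, and section 6.6 intends the analyses through visit 4 for publication.

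A second defence is that the bowel diary records more than leakage, and only leakage counts under section 6.3. This stands in part. The Visit 3 wording may bring other bowel symptoms into the decision, though, and every visit 2 item is still recorded after lead placement.

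A third is that dropping the visit 2 diary while keeping the visit 1 count leaves half the problem. This is correct, and the fix has to say so. A reader might infer from the AUC contrast of about 0.8 against 0.53–0.59 that the visit 1 count is nearly free of coupling. That contrast comes from assuming that the treatment effect is independent of baseline and that the only fluctuation is Poisson noise; it disappears under other plausible inputs.

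A reader might also infer that the models must fail to converge. The documents do not support that: they do not say that both values enter one model, and they allow departures from the strict rule.

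**Conclusion.** The concern holds, as a minor point. That the visit 2 bowel diary is an input to SNS success follows from sections 5, 6.3 and 6.6 alone and needs no simulation. Complete separation is certain only under the three conditions in step 3. Outside them its frequency depends on assumptions, and the percentages above should not be read as forecasts for this trial.

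Two stronger readings should be resisted. The overlap does not compromise the primary result: the endpoint, the sample size, the 90% credible interval and both stopping rules make no use of these models. Nor is the visit 2 bladder diary circular in the same sense: it does not define success, but as an on-stimulation measure it is not a pre-treatment predictor.

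**What to change.** In section 6.6, replace the sentence on the exploratory models with text to this effect:

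*Exploratory logistic regression models of SNS success will use only measures obtained before lead placement. The visit 2 bowel diary will not be used as a predictor of SNS success. The visit 1 bowel count is one term of the success rule, so its association with success is also partly definitional and it will not be reported as an independent predictor. Any association between the visit 2 bladder diary and SNS success will be reported descriptively as an on-stimulation correlate, with the number of patients lacking a post-lead diary.*

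No data collection, visit or sample size changes. The trial gives up one exploratory association, visit 2 bowel diary with SNS success, that is largely uninformative. The visit 2 bowel diaries can still be summarised descriptively, as section 6.6 plans for the secondary measures.
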